Principal Investigator: The PI will prepare, coordinate, conduct training onsite or online on each clinical site for protocol setting, and facilitate monthly meetings. The PI is one of the treating therapists. The PI will keep all electronic and paper based research data for seven years after data collection is completed.

Study coordinator: The study coordinator will keep all electronic and paper based research data until data collection is completed, and will conduct follow-up phone calls after four weeks of discharge to obtain the IPAQ scores. The study coordinator will perform review preparatory to research and will be mailing letter of invitation and informed consent form to potential participants prior to initial evaluation. Once a signed consent form is obtained, the study coordinator will conduct a retrospective chart review on the subject's initial evaluation and first follow-up visit if applicable, complete the Inclusion/Exclusion form, and determine the eligibility of the subject to participate in the study. The Study Coordinator is expected to attend the monthly meeting.

Research Staff: Treating physical therapists are expected to undergo training during the protocol setting and to attend the monthly meeting. They are responsible in recruiting participants, obtaining informed consent, conducting follow-up phone call prior to next visit, collecting the outcome scores for DGI, TUG, DHI, mCTSIB, IPAQ-short form questionnaire, and implementing the interventions.

Research Assistant. The Research Assistant can conduct a follow-up phone call to a potential participant to give opportunity for questions. This responsibility will be given to the research assistant upon completion of an informed consent training conducted by the principal investigator and passing a competency test on the informed consent.

Data Analysts: Electronic research data of the outcome measures will be forwarded to the data analysts from Adventist University for statistical analysis.

Equipment: The pedometers will be donated to the 54 participants who met the inclusion and exclusion criteria and randomized into one of the treatment groups, as a reward for participating in the research study and for them to perpetuate their physical activity.

Office and Filing Supplies: Under this category are office supplies for advertisement, recruitment, informed consent and outcome measure forms, training manuals, filing of research data.

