Shipping and Mailing Fees: These cover mailing of letter of invitations, result of the study and shipping of pedometers to participants who did not belong to the VRPW group.

Study Procedures

Subject Recruitment and Screening

The advertisement will contain brief information about the research project, inclusion criteria and contact information of the study coordinator and principal investigator for inquiries. Advertisement on the study will be in the form of the following: electronic flyers, print out flyers, news article and emails. The electronic flyer and news article will be disseminated as email attachment and links respectively, sent to referring physicians and senior groups in the community and postings in social media such as Florida Hospital Facebook page. The news article will be submitted to the Florida Hospital Sports Medicine and Rehabilitation newsletter.

The print out flyers will be posted at the reception area of participating clinics, doctor offices and senior group locations. The study coordinator will perform review preparatory to research for Florida Hospital sites. He will be mailing letter of invitation and informed consent form to potential participants prior to initial evaluation. The study coordinator or treating physical therapist will be giving letter of invitation and informed consent form to potential participants before or after the initial evaluation.

Consent Process

Informed Consent of subjects will be obtained in writing following HRP-802 INVESTIGATOR GUIDANCE: Informed Consent. This will be documented following the INVESTIGATOR GUIDANCE: Documentation of Informed Consent (HRP-803).

Documentation of Informed Consent Process

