Documentation of the informed consent process is required to establish that the subject was accurately and adequately informed and that no study-related procedures were initiated prior to obtaining informed consent. The research staff will complete the Documentation of Informed Consent Form (HRP-803) that contains the consent progress, date consent was obtained and that consent was obtained prior to initiating any research procedures. The research staff will explain the consent form to interested patients. A follow-up phone will be conducted by the principal investigator, research assistant or research staff to the potential participant prior to the beginning of the tenth visit. If the patient expressed willingness to take part in the research, the research staff will obtain a signature of subject during patient's visit/a face-to-face encounter with the patient. The study coordinator will perform a retrospective chart review on the subject's medical chart once a signed informed consent form is obtained.

Randomization

For the experimental design, block randomization will be performed to ensure

equal number of participants in each treatment group. The study coordinators will have a prerandomized masterlist of subjects generated using an online randomization program (<https://www.sealedenvelope.com/simple-randomiser/v1/lists>). The signed informed consent must be returned prior to tenth visit. Once the study coordinator confirmed that the subject is eligible to participate in the study by completing the Inclusion/Exclusion Form based on the retrospective chart review of the patient's medical record, he will assign the subject with an ID number and randomize the subject into one of the three groups as determined by the prerandomized master list: first intervention group (n=18, VR plus walking with pedometer, VRWP), second intervention group (n=18, VR plus walking instruction only, VRW) and control group (n=18, usual care, VR). The study coordinator will keep paper and electronic records that contain the list of research numbers with names of all the subjects, date of birth and medical record number.

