The VR (control) group will follow the conventional VR physical therapy without the encouragement of walking and without specification of walking in the home exercise program.

The use of an assistive device can be recommended for any subject in any group by the research staff to maximize safety. The patient may need to purchase the assistive device.

Participants who do not belong to the intervention group with pedometer will receive a pedometer after they completed the study. They will receive instructions on how to use the pedometer prior or on the day of their last visit.

Study Visits

For the experimental design that will be conducted at Florida Hospital locations, the following data will be collected as standard of care by the physical therapist during initial evaluation, and if more time is needed, during the first follow-up physical therapy appointment: mCTSIB, TUG, DGI, DHI, age, gender, body mass index, home situation, Functional Comorbidity Index (FCI) total, ability to drive, medications and insurance type. After the subject signs the informed consent, the study coordinator will be notified by the research staff to conduct a retrospective chart review on the physical therapy initial evaluation and first follow-up visit, if applicable, of the subject. The study coordinator will extract the following baseline measurements from the subject's medical record: DGI, mCTSIB, DHI, TUG and socio-demographic data that include age, gender, body mass index, home situation (lives alone or with social support), Functional Comorbidity Index (FCI) total, ability to drive (able or unable), medications for vertigo and insurance type (Medicare/Non-medicare). Based on the retrospective chart review, the study coordinator will determine if the subject is eligible to participate in the study.

Visit 1: Once the study coordinator determined that the subject is eligible to participate in the study, the subject will be assigned a research number and will be randomized into one of the three intervention groups. The research staff can initiate or continue the VR program. For the test-retest reliability of the TUG test, there will be one practice trial followed by two final performances that will be included in the data analysis. The subject will also be asked to complete the IPAQ-short form questionnaire. The test-retest reliability of TUG and the IPAQ-short form questionnaire are for research purposes only.

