Visit 2: The research staff can initiate the research intervention according to the intervention group.

Visit 3 to visit prior to discharge: The research staff can continue the VR and intervention according to the intervention group.

Discharge or last visit: All outcome measures (DGI, TUG, mCTSIB, DHI and IPAQ) will be reassessed. Discharge scores for DGI, TUG, mCTSIB and DHI are standard of care, while IPAQ is for research purposes only. The total number of visits and length of

interventions (in weeks) for every participant will be recorded as secondary outcome measures. These research data will be forwarded to the study coordinator, and will be stored in a locked cabinet and password protected Florida Hospital computer.

Four-weeks after discharge: The study coordinator will conduct a follow up phone call to all subjects four weeks after discharge summary is completed to obtain the level of physical activity using the IPAQ short form questionnaire. This is for research purposes only. A follow-up on a subject will be discontinued if a subject is not reached after three attempts of follow-up phone call made on three different days between 30 and 45 days. Data analysis will commence once all the data from 54 subjects are collected.

Table 1. Summary of Interventions for VRWP, VRW and VR Groups.

VRWP (n=18)	VRW (n=18)	VR (n=18)

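### Allocation is not concealed from the study coordinator, who holds the list, settles eligibility and assigns the arm, and who later takes the four-week IPAQ knowing that arm

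*Combined protocol and SAP*

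**What the plan says.** The relevant duties are spread over several sections but fall to one role.

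- **Holding the list.** Randomization: "The study coordinators will have a prerandomized masterlist of subjects", generated with an online program. Allocation is blocked, with 18 subjects per arm. No block size is given.
- **Inviting.** Subject Recruitment and Screening: "The study coordinator or treating physical therapist will be giving letter of invitation and informed consent form to potential participants". The coordinator also mails invitations ahead of the initial evaluation.
- **Deciding eligibility.** Resources Available has the coordinator complete the Inclusion/Exclusion form and "determine the eligibility of the subject to participate in the study" once consent is signed. Study Visits repeats it: "Based on the retrospective chart review, the study coordinator will determine if the subject is eligible to participate in the study". In the same chart review the coordinator extracts baseline DGI, mCTSIB, DHI and TUG.
- **Assigning.** Randomization: once eligibility is confirmed, "he will assign the subject with an ID number and randomize the subject into one of the three groups", following the master list. Data De-identification adds that the research number itself derives from the randomization list and that the coordinator keeps the key linking names to numbers.
- **Collecting the four-week outcome.** Study Visits: "The study coordinator will conduct a follow up phone call to all subjects four weeks after discharge summary is completed", to obtain the IPAQ short form.

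Consent is explained and obtained by the research staff, who are the treating therapists. No section describes sealed envelopes, release of assignments by another party, or an assessor unaware of the arm.

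**The concern.** Random assignment protects a comparison only if whoever decides on entry cannot know the next arm when deciding. Here the person who confirms that a consented subject may enter also holds the list that fixes the arm, and has that subject's baseline balance and handicap scores in hand. Knowledge of prognosis and of the next arm can therefore meet in one person before the decision is final. With 18 subjects per arm, a few entries accepted, declined or reordered could alter the make-up of an arm.

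The second issue is separate. The four-week IPAQ is a recall questionnaire about walking and other activity, and Study Objectives names it as a time point for the pedometer question. A caller who assigned the arm can, without intending it, prompt or interpret answers differently by arm.

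**Working it through.** The plan gives no figure to reproduce, so the check follows the order of events and asks what the coordinator can know and decide at each step.

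1. **Invitation.** The coordinator or a therapist invites. Mailed invitations precede the initial evaluation, so that evaluation's scores do not yet exist. Study Site(s)/Location(s) and Number of Subjects plans consecutive admissions. Discretion here is small.
2. **Consent.** Therapists obtain it. Nothing says that they see the list. Randomization lets consent be returned at any time before the tenth visit, so the moment at which a subject becomes ready for assignment can vary widely.
3. **Eligibility.** The coordinator decides from the chart, after consent. Under Exclusion Criteria, the exclusion for unstable medical issues is determined and documented by the evaluating therapist. Other items (blood pressure, positional tests, central diagnoses, syncopal falls) are largely charted facts. The coordinator still reads the chart and makes the final determination.
4. **Order of entry.** No rule says that consented subjects are processed in order of consent. If two are waiting, the coordinator chooses who takes the next line of the list.
5. **Assignment.** The coordinator reads the arm from the list. No step hides the next line until step 3 is recorded.
6. **Four-week call.** The caller is the person who made the assignment and keeps the key of names to numbers, so the caller knows the arm.

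Steps 3 and 4 are where selection remains possible. Step 6 is where interviewer influence is possible.

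**How predictable the next arm is (illustration; the block sizes are assumptions).**

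- No list and no knowledge of past assignments: 1/3, or 33%.
- No list, but past assignments and block size known, always guessing the arm with most places left. For blocks of 3 the chances of a correct guess are 1/3, 1/2 and 1, so the average is (1/3 + 1/2 + 1)/3 = 0.61. Simulation of 20,000 blocks gives about 0.61 for size 3, 0.56 for size 6 and 0.53 for size 9.
- List readable in sequence: no guessing is needed.

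The middle line is why block sizes should vary and stay undisclosed even after the list is moved. Therapists know the arms they deliver and could reconstruct part of a fixed-block sequence.

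**The case against.** The strongest reply is that the coordinator has little room to act. Admissions are meant to be consecutive, therapists obtain consent, mailed invitations go out before the evaluation's scores exist, and most exclusions are charted findings. Wrongly excluding a consented subject would leave a signed consent and a completed Inclusion/Exclusion Form. All of this stands, and it narrows the concern to chart interpretation and order of entry. It does not supply concealment: the plan relies on the list holder's conduct where a procedural barrier would normally be in place.

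Several stronger readings are tempting but not supported:

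- A reader might infer that the coordinator judges whether medical issues are unstable. Exclusion Criteria gives that judgement to the evaluating therapist.
- A reader might infer that the list is known to be on open display and every assignment foreseen. The documents do not say how it is displayed. They say that the coordinator has it and assigns from it, with no masking step.
- A reader might express the risk as a share of the planned effect (F=.25) by supposing that a few frail candidates are steered away from one arm. The documents give no basis for such a scenario. A shift in baseline mean also does not carry one-for-one into the group-by-time analysis in the Statistical Analysis Plan or the pretest-posttest differences in Data Analysis.
- A reader might say that no analysis could help. Imbalance on measured baseline scores can be partly adjusted for. However, the planned ANCOVA adjusts only for age, the between-group tests in Data Analysis are Kruskal-Wallis without covariates, and selection on unmeasured factors would remain.

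On the IPAQ, it is fair to say that subjects know their own arm, so an unaware caller would not remove reporting bias. Treating therapists also collect the discharge IPAQ and all the primary outcomes, so unblinded assessment is wider than this call.

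**Conclusion.** The concern holds in limited form. The stated procedure gives one role the list, the final eligibility decision and the assignment, with no concealment step between them, and gives the same role an outcome call made with knowledge of the arm. This is more than missing detail, because the text assigns these duties explicitly. It shows that bias is possible, not that it occurred, and its size cannot be estimated from the documents.

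The conclusion assumes that the coordinator role is one person, or several people sharing the duties. Randomization uses the plural once; elsewhere the role is singular, and nothing separates list holder, screener and caller. It also assumes that no undocumented masking of the list was in use.

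**What to change.** **Randomization.** Have a person with no recruitment, eligibility, treatment or outcome-analysis role, or an online release service, generate and hold the list with varying, undisclosed block sizes. Release each assignment, by sequentially numbered opaque envelope or online, only after the Inclusion/Exclusion Form is signed and dated. Enter subjects in order of consent. The data analysts should not hold the list, because that would tie knowledge of allocation to the outcome analysis.

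**Data De-identification.** Do not take research numbers from the randomization list.

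**Resources Available and Study Visits.** Move the four-week IPAQ call to the existing Research Assistant, not told the arm and working from a fixed script. The current remit is narrower ("The Research Assistant can conduct a follow-up phone call to a potential participant to give opportunity for questions"), so the role description must be extended and IPAQ training added. This reduces interviewer bias only; reporting bias by subjects who know their arm remains.

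**Cost.** Protocol wording, one extra step per assignment, brief IPAQ training, and naming an independent list holder or service. Visits and sample size do not change.

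**If enrolment is complete.** Data Analysis is written in the past tense, so this may apply. In that case, report the lack of concealment and of an unaware caller as limitations, and list consented-but-excluded subjects with reasons and dates.

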There are four purposes to this study. The primary purpose of this study is to evaluate the impact of walking as an exercise component of VR on both primary and secondary vestibular-specific outcome measures. The primary outcomes are mCTSIB, TUG test, DGI, and DHI, while the secondary outcomes are the total number of visits and length of interventions (in weeks). The second purpose is to evaluate whether pedometers increase the adherence of older adults with vestibular issues to a walking program. This will be measured by change in physical activity, as represented by International Physical Activity Questionnaire (IPAQ) Walking Metabolic Equivalent of Task (MET)-minutes/week and IPAQ Total Physical Activity MET-minutes/week scores from the IPAQ short form during the episode of care (admission and discharge) and on four-weeks follow-up compared to those patients who only received instructions to walk without a pedometer. The third purpose of this study is to establish test-retest reliability of the TUG test on older adults with dizziness. Lastly, the fourth purpose of this study to investigate if the TUG, DGI, and mCTSIB are significant and strong predictors of the DHI in older adults with dizziness. Protocol #1365169 “Predictors of Disability in the Older Adults” is being performed to supplement the number of subjects for the fourth objective of this study.

Study Design

Research Design

1. Experimental Design. To answer the first and second study objectives, a pragmatic, randomized, prospective, clinical study on 54 older adults with dizziness will be utilized. This will be conducted at Florida Hospital Sports Medicine and Rehabilitation locations that offer vestibular therapy. These are in East Orlando and Winter Park.
2. Correlation Design. A correlation analysis will be performed on the data collected on 54 subjects in the experimental design to establish the test-retest reliability of the Timed Up and Go.
3. Cross-sectional Descriptive Design. A regression analysis will be performed on three predictors of the Dizziness Handicap Inventory, obtained from the data collected on 54 subjects in the experimental design and from Florida Hospital Sports Medicine and Rehabilitation Physical Therapy medical charts from June 2015 to June 2018 that met the inclusion and exclusion criteria that were outlined in the Protocol #1365169.

Study Agent, Device, and/or Intervention Description

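### Late consent can put up to about nine ordinary VR visits between the primary-outcome baseline and the start of walking, diluting the walking effect and adding noise without biasing the allocation

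*Combined protocol and SAP*

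**What the plan says.** **Consent.** The Randomization section states: "The signed informed consent must be returned prior to tenth visit". Documentation of Informed Consent Process places the follow-up call "prior to the beginning of the tenth visit", and the signature is taken face to face: "the research staff will obtain a signature of subject during patient's visit/a face-to-face encounter with the patient". Resources Available differs. Among the research staff's duties it lists "conducting follow-up phone call prior to next visit".

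**Randomisation.** It comes after signed consent, chart review and confirmation of eligibility. No deadline is given for randomisation itself.

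**Baseline.** Under Study Visits: "The study coordinator will extract the following baseline measurements from the subject's medical record: DGI, mCTSIB, DHI, TUG". Those values were measured at the initial evaluation or, if time ran short, at the first follow-up appointment.

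**Treatment.** At study Visit 1, "The research staff can initiate or continue the VR program", so VR before assignment is foreseen. At study Visit 2, "The research staff can initiate the research intervention according to the intervention group". The IPAQ is completed at study Visit 1. TUG is also performed there, but for reliability only.

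**Analysis.** The Statistical Analysis Plan specifies repeated-measures ANCOVA adjusted for age. Data Analysis, Objective 1, reports pretest-to-posttest differences compared by Kruskal-Wallis, with Wilcoxon signed rank tests within groups. Neither takes account of therapy received before randomisation. The secondary outcomes, number of visits and weeks of intervention, have no stated start point.

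**The concern.** Objective 1 asks what walking adds to VR. That contrast can be informed only by what happens after the arms diverge, at study Visit 2. For a subject who consents late, much of the measured change may already have occurred under ordinary VR, and little of the episode is left for walking to act. If many subjects are like this, a real walking effect would appear smaller than it is. A null result could then not be separated from short exposure.

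**Working it through.** The plan gives no figure for entry timing, episode length or exposure, so there is none to reproduce. The visit count follows from the text. The rest is illustration under stated assumptions.

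**1. Visit count.** Call the initial evaluation therapy visit 1.
- The last face-to-face chance to sign before the tenth visit is visit 9.
- Chart review and randomisation follow, so study Visit 1 is visit 10 at the earliest, and walking starts at visit 11.
- Visits 2 to 10 are nine ordinary VR visits between baseline and walking.
- The gap is one shorter if baseline was completed at the first follow-up. It is one longer if the evaluation is not numbered as a visit, and may be longer still because randomisation has no deadline.

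**2. Exposure.** Assume an episode of N visits, randomisation at visit k, walking from visit k+1, and benefit proportional to the visits left before the discharge visit. Exposure relative to entry at visit 1 is (N − 1 − k)/(N − 2).
- N = 12: k = 9 gives 2/10 = 0.20. The mean over k = 1 to 9 is (11 − 5)/10 = 0.60.
- N = 20: k = 9 gives 10/18 = 0.56. The mean is (19 − 5)/18 = 0.78.
- Milder case: three quarters enter at visit 1 and one quarter at visits 5 to 9. For N = 12 the late group averages (11 − 7)/10 = 0.40, so overall 0.75 + 0.25 × 0.40 = 0.85. For N = 20 it averages 12/18 = 0.67, so overall 0.75 + 0.25 × 0.67 = 0.92.

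**3. Power, for scale only.** The reference case is a group-by-time test with f = .25 (from Sample Size Determination), two time points, an assumed correlation of 0.5, and 48 completers (54 × 0.9 = 48.6, taken as 16 per arm). Power is 0.86. Now spread 0 to 9 pre-walking visits evenly over an episode of T visits and take the effect as proportional to the share of visits that remain, on average (T − 4.5)/T:
- T = 12: share 0.625, f = 0.25 × 0.625 = 0.156, power 0.45.
- T = 20: share 0.775, f = 0.25 × 0.775 = 0.194, power 0.64.

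The 0.86 is not the plan's own 0.80. The plan does not state the test, number of time points or correlation behind 54, so its calculation cannot be confirmed.

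**4. Noise and chance imbalance.** If pre-randomisation visits are spread evenly over 0 to 9, their SD is √(99/12) = 2.87. The standard error of the difference in mean prior visits is 2.87 × √(2/18) = 0.96 visits for 18 versus 18. For the pooled walking groups against control it is 2.87 × √(1/36 + 1/18) = 0.83. A chance difference of a visit or more is therefore quite possible.

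**5. Secondary outcomes.** If total visits include the earlier ones, and later visits are independent of them with SD 3 to 5, the variance rises by (9 + 8.25)/9 = 1.92 to (25 + 8.25)/25 = 1.33. If episode length is fairly fixed, the reverse can hold, and the count from randomisation is the noisier one. The documents do not say which applies.

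**6. Direction of error.** Assignment is made after the chart baseline and after the prior VR, so neither can depend on arm. The expected between-group difference in prior VR is zero. The within-group Wilcoxon tests have no such protection: each arm's pretest-to-posttest change includes whatever VR achieved before assignment.

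**The case against.** The strongest reply is that allocation remains fair. A reader might infer that late entry biases the walking comparison. It does not, because prior VR is balanced in expectation. In a trial described as pragmatic, a baseline at the start of the care episode is a defensible choice. This stands, and it limits the between-group harm to dilution, noise and chance imbalance.

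Second, the tenth visit is a permitted maximum. Invitations go out before the initial evaluation or are handed over around it, and one section ties the follow-up call to the next visit. Most subjects may enter early. This also stands, although the tenth-visit limit appears twice and cannot be dismissed as a slip.

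Third, walking is a daily home programme, so benefit proportional to remaining clinic visits is only a convenience. The exposure and power figures are therefore no more than illustrations.

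Fourth, a reader might infer that visits before randomisation are counted in the secondary outcomes. The documents do not establish this. It is the natural sense of a total, but the numbered schedule begins at study Visit 1. The defect is an undefined start point.

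Fifth, the IPAQ starts at a different time from the primary outcomes. They are analysed separately, so this does no harm in itself.

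**Conclusion.** The point holds as a matter of dilution, noise and interpretation. The text allows up to about nine ordinary VR visits between the primary-outcome baseline and the start of walking, and neither the planned nor the reported analysis takes account of them. Mean exposure would be about 60% to 78% under even entry over visits 1 to 9 with 12- to 20-visit episodes, and 85% to 92% if only a quarter enter at visits 5 to 9. These figures rest on an assumed episode length, entry pattern and proportional benefit, none of which the documents give.

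A reader might go further and convert the 60% into a sample-size multiple (1/0.60² = 2.8). That needs both a 12-visit episode and even entry, so it should not be presented as a finding. What can be said is that a null result on Objective 1 should not be described as walking adding nothing unless exposure is reported beside it.

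**What to change.** 1. **Record and adjust.** Record each subject's therapy visits and weeks before randomisation, and include this as a covariate for the four primary and both secondary outcomes. In the repeated-measures ANCOVA it must interact with time, or it will not affect the change contrast. Kruskal-Wallis takes no covariate, so a rank-based ANCOVA or a rank test stratified by prior visits would be needed. Add a sensitivity analysis limited to early entrants. Data Analysis is written in the past tense, so label these analyses post hoc if the data have been analysed. The dates should be recoverable from the chart, but the documents do not say that visit number at randomisation is recorded.

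2. **Baseline for future subjects.** Take all four measures at study Visit 1 in every subject, before allocation is revealed. Doing so only for late entrants would mix baseline dates. Revealing allocation first would leave the baseline to treating therapists who know the arm. Study Visits lists randomisation before the TUG and Table 1 lists it after, so the two must be reconciled. The cost is a few minutes of repeat testing, since TUG is already performed there. This removes pre-assignment recovery from the change scores but does not restore lost exposure.

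3. **Secondary outcomes.** State the start point and report the pre- and post-randomisation parts separately. In a linear model with prior visits as covariate, the group contrast for visits is the same whether the total or the post-randomisation count is used. The cost is wording only.

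4. **Consent timing.** Reconcile Resources Available with the two statements of the tenth-visit limit, and seek consent as early as recruitment allows. Only this addresses dilution directly. A hard early cut-off could lose patients who are slow to decide, so it has to be weighed against recruitment.
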